| p-value             |                    | x.xxxx           |
| Month 12            | xx (xx.x%)         | xx (xx.x%)       |
| Odds Ratio*         |                    |                  |
| Odds Ratio (95% CI) |                    | x.xx (x.xx,x.xx) |
| p-value             |                    | x.xxxx           |
| Month 24            | xx (xx.x%)         | xx (xx.x%)       |
| Odds Ratio*         |                    |                  |
| Odds Ratio (95% CI) |                    | x.xx (x.xx,x.xx) |
| p-value             |                    | x.xxxx           |

\*Logistic regression model includes treatment as factor and baseline BCVA as covariate

**Table 14.2-26 Proportion of patients with IRF at baseline who never resolve their IRF (irrespective of their SRF) – Logistic Regression**

Full Analysis Set

|                     | Intensive
(N=X) | Relaxed
(N=X) |
|---------------------|--------------------|------------------|
| Month 2             | xx (xx.x%)         | xx (xx.x%)       |
| Odds Ratio*         |                    |                  |
| Odds Ratio (95% CI) |                    | x.xx (x.xx,x.xx) |
| p-value             |                    | x.xxxx           |
| Month 12            | xx (xx.x%)         | xx (xx.x%)       |
| Odds Ratio*         |                    |                  |
| Odds Ratio (95% CI) |                    | x.xx (x.xx,x.xx) |
| p-value             |                    | x.xxxx           |
| Month 24            | xx (xx.x%)         | xx (xx.x%)       |
| Odds Ratio*         |                    |                  |
| Odds Ratio (95% CI) |                    | x.xx (x.xx,x.xx) |
| p-value             |                    | x.xxxx           |

\*Logistic regression model includes treatment as factor and baseline BCVA as covariate

**Table 14.2-27 Proportion of patients with IRF and SRF at baseline who never resolve either their IRF or SRF – Logistic Regression**

Full Analysis Set

|                     | Intensive
(N=X) | Relaxed
(N=X) |
|---------------------|--------------------|------------------|
| Month 2             | xx (xx.x%)         | xx (xx.x%)       |
| Odds Ratio*         |                    |                  |
| Odds Ratio (95% CI) |                    | x.xx (x.xx,x.xx) |
| p-value             |                    | x.xxxx           |
| Month 12            | xx (xx.x%)         | xx (xx.x%)       |
| Odds Ratio*         |                    |                  |

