2.4.1.2 Post-baseline

All assessments obtained after the date of first dose of study drug are considered as post-baseline unless otherwise specified. Missing data for post-baseline values, for example due to discontinuation, loss to follow-up, or other types of censoring (e.g. due to rescue medication), will not be imputed. Only subjects with measurements at any given time point will be included in the analysis for that given parameter and visit. Refer to Section 2.4.3 for further details regarding the handling of missing dates.

The study day for a baseline or post-baseline scheduled or unscheduled visit is defined as:

$$\text{Study day} = (\text{Date of visit}) - (\text{date of first treatment}) + 1$$

The study day for a scheduled or unscheduled visit before baseline is defined as:

$$\text{Study day} = (\text{Date of visit}) - (\text{date of first treatment})$$

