2.8.1 Variables

The primary efficacy variable and key secondary variables are:

- Mean change in BCVA from baseline to month 24
- Mean change in BCVA from baseline to month 12
- Mean change in central retinal thickness from baseline to month 12 and month 24
- Number of injections from baseline to month 12 and 24

The additional secondary variables are:

- Mean change in area of new and existing geographic atrophy from baseline to month 12 and 24.

Patients at sites where autofluorescence can be undertaken will be assessed for the presence of geographic atrophy at Baseline, visit 4 (week 8) and then again at the 12 and 24 month visits. If present, the area of geographic atrophy will be estimated.

- New Geographic Atrophy at month 12 and month 24^a (Yes, No)
 - Change in area of geographic atrophy from the visit where geographic atrophy was first present
- Intra-retinal (IRF) and Sub-retinal fluid (SRF) (present/absent)

At each relevant assessment visit, the patient is examined for the presence/absence of IRF and SRF by the central reading centre as per the definitions for their treatment arm.

- The proportion of patients showing no IRF and SRF at month 2, 12 and 24
- Proportion of patients showing greater than or equal to 15 letters (EDTRS) gain and less than 15 letters loss from baseline to month 24.
- Proportion of patients with SRF as assessed by the [REDACTED] CRC and IRF as assessed by Investigators at baseline who do not resolve their SRF and IRF by Month 24

The remaining exploratory variables are:

- Proportion of patients with a) SRF, b) IRF, c) both SRF and IRF, d) neither SRF and/or IRF at baseline, month 2, 12 and 24
- Proportion of patients with $\geq 6/12$ visual acuity at baseline, month 12 and month 24
- Proportion of patients with 6/60 or worse visual acuity at baseline, month 12 and 24
- The proportion of patients with IRF and SRF at baseline who never resolve either their IRF or SRF at any visit up to Month 2, 12 and 24.
- Proportion of patients with SRF at baseline who never resolve their SRF at any visit up to Month 2, 12 and 24 (irrespective of their IRF)
- Proportion of patients with IRF at baseline who never resolve their IRF at any visit up to Month 2, 12 and 24 (irrespective of SRF)

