Proportion of patients with IRF at baseline who never resolve their IRF at any visit up to Month 2, 12 and 24 (irrespective of SRF)	1. Logistic regression model (Refer to Section 2.8.2.8)
Proportion of patients with IRF and SRF at baseline who never resolve either their IRF or SRF at any visit up to Month 2, 12 and 24.	1. Logistic regression model (Refer to Section 2.8.2.8)
Proportion of patients who show $\geq 6/12$ visual acuity at baseline, month 12 and 24	1. Logistic regression model (Refer to Section 2.8.2.8)
Proportion of patients who show 6/60 or worse visual acuity at baseline, month 12 and 24	1. Logistic regression model (Refer to Section 2.8.2.8)
Time to Breakpoint	1. Kaplan Meier Survival Analysis (Refer to Section 2.8.2.10)

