2.8.2.8 Logistic regression

The logistic regression models to be fitted are detailed in Table 2.8.2.8-1.

Table 2.8.2.8-1 Logistic Regression Models

Model Number	Outcome Variable	Predictor/Covariate	
		Mandatory	Optional
LR_1	Newly developed geographic atrophy between baseline and Month 12 / 24 (Yes/No)	Treatment	Baseline geographic atrophy Baseline IRF/SRF Centre
LR_2	≥ 15 letter increase from baseline to month 24 (Yes/No)	Treatment	Baseline BCVA Centre
LR_3	SRF and IRF at baseline and never resolving SRF at any visit up to Month 2 (Yes/No) Same for Month 12 and 24	Treatment	Baseline IRF/SRF Centre
LR_4	Greater than or equal to 15 letters (EDTRS) gain and less than 15 letters loss from baseline to month 24	Treatment	Baseline BCVA Centre
LR_5	SRF as assessed by the ██████████ CRC and IRF as assessed by Investigators who do not resolve their SRF and IRF by Month 24	Treatment	Baseline IRF/SRF Centre
LR_6	No IRF and SRF at month 2, 12 and 24	Treatment	Baseline IRF/SRF Centre
LR_7	SRF (as assessed by the ██████████ CRC) and IRF (as assessed by Investigators) who do not resolve their SRF and IRF by Month 24	Treatment	Baseline IRF/SRF Centre
LR_8	IRF at baseline who never resolve their IRF at any visit up to Month 2, 12 and 24 (irrespective of SRF)	Treatment	Baseline IRF Centre

Model Number	Outcome Variable	Predictor/Covariate	
		Mandatory	Optional
LR_9	IRF and SRF at baseline who never resolve either their IRF or SRF at any visit up to Month 2, 12 and 24.	Treatment	Baseline IRF/SRF Centre
LR_10	Show $\geq 6/12$ visual acuity at baseline, Month 2, Month 12, month 24	Treatment	Baseline BCVA Centre
LR_11	Show 6/60 visual acuity or worse at baseline, Month 2, Month 12, month 24	Treatment	Baseline BCVA Centre

From each model the adjusted odds ratio for the outcome variable, for intensive compared with relaxed treatment, will be obtained with 2-sided 95% confidence limits.

Using PROC GENMOD to calculate the 95% confidence interval for the odds ratios assumes asymptotic normality of the Wald estimate for the regression coefficient. The 95% confidence interval for the regression parameter of the relaxed regime treatment effect relative to the intensive regime is calculated using an exponential transformation to create the 95% confidence interval for the odds ratio.

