2.12 Sample size and power considerations

This study is designed as a non-inferiority trial. The non-inferiority limit for the difference between groups (change with intensive treatment – change with relaxed treatment) is 5.

Therefore, if the upper 2-sided 95% confidence limit for the difference between treatments (intensive – relaxed) in the change in BCVA (on treatment – baseline) is < 5 the relaxed treatment will be declared non-inferior to the intensive treatment.

Assuming a Standard Deviation (SD) of 15 (as used in the CATT study; Martin et al, 2012) and assuming no true difference between treatments, a sample size of 165 patients per group provides 80% power assuming analysis will be conducted using a t-test. The sample size of 165 per group (total of 330) will be randomised (this allows for 15% drop-out based on the CATT study which observed an 11% dropout in the ranibizumab as needed group and 16% in the bevacizumab as needed group over the two years in the study). Calculations were performed using SAS V9.3.

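### The exploratory 'never resolved fluid by Month 12 and 24' endpoints are fitted as plain yes/no outcomes, with no allowance for unequal follow-up and no rule for patients who leave with fluid

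*SAP*

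**What the plan says.** SAP 2.8.1 lists three cumulative fluid outcomes among the exploratory variables. The SRF one counts patients with SRF at baseline "who never resolve their SRF at any visit up to Month 2, 12 and 24 (irrespective of their IRF". Table 2.8.2-3 repeats the IRF one as "Proportion of patients with IRF at baseline who never resolve their IRF at any visit up to Month 2, 12 and 24 (irrespective of SRF", and row LR_9 of Table 2.8.2.8-1 gives the combined one as "IRF and SRF at baseline who never resolve either their IRF or SRF at any visit up to Month 2, 12 and 24".

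Table 2.8.2-3 assigns one method to all three: logistic regression. In Table 2.8.2.8-1 the models contain treatment, with baseline fluid and centre optional. The shells (Tables 14.2-25 to 14.2-27, headed Full Analysis Set) state: "Logistic regression model includes treatment as factor and baseline BCVA as covariate". Neither place has a follow-up time, an offset or a censoring rule, and the shells give no denominator rule.

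The one general rule on missing post-baseline data is in SAP 2.4.1.2. It rules out imputation and adds: "Only subjects with measurements at any given time point will be included in the analysis for that given parameter and visit".

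Other endpoints that depend on follow-up are treated differently:
- Newly developed geographic atrophy gets logistic regression and survival analysis (Table 2.8.2-2).
- Time to breakpoint gets Kaplan-Meier (Table 2.8.2-3).
- Injection counts get a log-time offset (2.8.2.7).

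**The concern.** Whether an eye has ever been seen without fluid depends on how long it was imaged. The FAS needs only one post-baseline BCVA value (SAP 2.2), so early leavers belong to it. Take a patient with SRF at baseline who still has SRF at Week 8 and leaves at Month 4. That patient has resolved at no visit up to Month 24. On the literal definition this is a never-resolved case at Months 12 and 24 after four months of observation.

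The rule in 2.4.1.2 suits a status measured at a visit. It does not say what to do with an outcome accumulated over all visits up to a date. Two programmers could follow this SAP and print different tables.

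Fluid tolerance is what separates the two regimens, so these tables will be read as how often each regimen fails to dry the retina. On the literal reading, persistent fluid and early departure are mixed. A difference in drop-out between arms would then appear as a difference in fluid.

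**Working it through.** **The plan's own drop-out figure.** SAP 2.12 is the only place a drop-out rate is used. Inputs: margin 5 letters, SD 15, true difference 0, two-sided alpha 0.05, power 80%.

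n per arm = 2 × (1.960 + 0.842)² × 15² / 5² = 141.3, so 142 evaluable. Allowing for 15% drop-out gives 142/0.85, so 168, or 142 × 1.15, so 164. The plan states 165. With 165 × 0.85 ≈ 140 evaluable per arm, t-test power is 79.4%. The figure reproduces, and 15% is the plan's working rate. The plan bases it on a cited trial that "observed an 11% dropout in the ranibizumab as needed group and 16% in the bevacizumab as needed group over the two years". No Month 12 rate is given.

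**Inputs for the bias.** From the documents: drop-out d = 15%, with 11% and 16% as the cited range. Assumed, because the documents are silent: the true never-resolved proportion p at Month 24, the curve S(t) of eyes still unresolved, leaving times uniform over 24 months, and leaving unrelated to resolution.

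**Literal reading (unresolved leavers count as never resolved).** Let E be the average of S over the leaving times.

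Counted proportion = p + d × (E − p)

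Relative overstatement = d × (E/p − 1)

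*Constant resolution hazard.* E = (1 − p)/(−ln p). For p = 0.05: E = 0.95/2.996 = 0.317, and 0.15 × (0.317/0.05 − 1) = 0.80.

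| True p | E | Counted, d = 15% | Overstated, d = 11% | d = 15% | d = 16% |
|---|---|---|---|---|---|
| 5% | 0.317 | 9.0% | +59% | +80% | +86% |
| 10% | 0.391 | 14.4% | +32% | +44% | +47% |
| 20% | 0.497 | 24.5% | +16% | +22% | +24% |
| 30% | 0.581 | 34.2% | +10% | +14% | +15% |
| 50% | 0.721 | 53.3% | +5% | +7% | +7% |

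*Early resolution.* Suppose eyes that resolve do so with a mean of 2 months, and the rest never do: S(t) = p + (1 − p)exp(−t/2). Then E = p + (1 − p)(2/24)(1 − exp(−12)). At d = 15% the overstatement is +24% for p = 5%, +11% for 10%, +3% for 30% and +1% for 50%.

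*Effect on the odds ratio.* Give both arms the same constant-hazard curve, with 11% drop-out in one and 16% in the other. For p = 5% the counted proportions are 7.94% and 9.27%, so the odds ratio is (0.0927/0.9073)/(0.0794/0.9206) = 1.19 with no true difference. For p = 10% it is 1.13, and for p = 50% it is 1.05. The 11% against 16% split is illustrative; the plan predicts no difference between arms.

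**Reading 2.4.1.2 as requiring a measurement at the stated month.** If leaving is unrelated to resolution, those measured at Month 24 have never-resolved proportion p, so the bias is 0. The share of eyes discarded although already seen to resolve is d × (1 − E). At d = 15% this is 0.15 × 0.683 = 10.2% for p = 5% and 0.15 × 0.279 = 4.2% for p = 50%.

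**Mixed rule (drop unresolved leavers, keep resolved ones).** The proportion becomes p(1 − d)/(1 − dE). Relative to p, at d = 15%, this is 0.85/(1 − 0.15 × 0.317) − 1 = −10.8% for p = 5%, and −4.7% for p = 50%. This rule biases the result downwards.

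**Model rows.** LR_8 matches the IRF endpoint and LR_9 the combined one. The nearest row for SRF is LR_3: "SRF and IRF at baseline and never resolving SRF at any visit up to Month 2 (Yes/No". It requires both fluids at baseline, so no row matches the SRF endpoint that ignores IRF, although Table 14.2-25 reports it.

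**The case against.** The strongest objection is that the plan nowhere says a leaver with fluid is counted as never resolved. The one general rule points towards leaving out patients not measured at the time point, and on that reading the bias is zero under independent leaving. This stands. A reader might infer that the plan instructs the biased count, but the text leaves the classification open.

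The second objection is that drop-out rates alone do not give a size. This also stands. A reader might infer a large overstatement, approaching a doubling, from the 11% to 16% figures. Under constant hazard at 15% drop-out, a 95% overstatement needs a true proportion near 4%, and even a 15% overstatement needs one below about 28%. The documents give no such proportion, resolution curve or pattern of leaving. The relative figures also look larger than the absolute ones: the +80% case is 5% becoming 9%.

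Third, Kaplan-Meier and Cox need non-informative censoring, an assumption comparable to the one needed by the completer analysis. This is true. The gain is that all observed follow-up is used and the denominator is explicit.

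Fourth, the endpoints are exploratory, and fluid is covered elsewhere: the secondary endpoint of no IRF and SRF, the by-visit proportions, optional GEE and random-intercept models, planned missing-data sensitivity analyses and an optional per-protocol run. These limit the harm. The by-visit models, however, describe presence at each visit and do not answer the never-resolved question.

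**Conclusion.** The point holds in a limited form. Three cumulative fluid outcomes are analysed only as yes/no logistic outcomes, with no allowance for unequal follow-up and no rule for patients who leave with fluid. The literal definition overstates the Month 24 proportion by about 7% to 80% in relative terms at 15% drop-out, for true proportions of 50% down to 5%. That range assumes a constant hazard and uniform, independent leaving, and the figures fall to about 1% to 24% under the early-resolution curve above. Requiring a measurement at the stated month removes the bias if leaving is unrelated to fluid, at the cost of discarding about 4% to 10% of eyes already seen to resolve. No Month 12 size can be derived without a Month 12 drop-out rate.

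The plan should be changed because a better method is already in the SAP and already used for a similar cumulative outcome, new geographic atrophy. Nothing here touches the primary BCVA comparison.

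**What to change.** In SAP 2.8.2.8, Table 2.8.2-3 and Tables 14.2-25 to 14.2-27:

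- Define the risk set as eyes with the fluid in question at baseline, and print it as the denominator.
- Analyse time to first reading-centre grading without that fluid, censored at the last gradable OCT. For the combined endpoint, state what counts as resolution.
- Report the Kaplan-Meier proportion unresolved at Months 2, 12 and 24 with 95% CI, and the arm comparison from a Cox or discrete-time model, under 2.8.2.10. This may replace the logistic model or stand beside it, as for new geographic atrophy.
- If the logistic model stays, state the classification of leavers and the denominator. Do not remove only the unresolved leavers, because that biases the result low.
- Add a model row for SRF at baseline irrespective of IRF, or correct LR_3.

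The cost is SAP wording and three shells. OCT dates and gradings are already collected. A hazard ratio or Kaplan-Meier difference replaces or joins the odds ratio, and the non-informative censoring assumption should be stated.

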**Table 14.2-7 Interval Decision Summary Table**

Full Analysis Set

| Visit  | Interval Decision*                     | Intensive
(N=X) | Relaxed
(N=X) | Total
(N=X) |
|--------|--|--------------------|------------------|----------------|
| Week 8 |  |                    |                  |                |
|        | Loss in VA                             | x (xx.x)           | x (xx.x)         | x (xx.x)       |
|        | Haemorrhage                            | x (xx.x)           | x (xx.x)         | x (xx.x)       |
|        | IRF/SRF                                | x (xx.x)           | x (xx.x)         | x (xx.x)       |
|        | Loss in VA AND Haemorrhage             | x (xx.x)           | x (xx.x)         | x (xx.x)       |
|        | Loss in VA AND IRF/SRF                 | x (xx.x)           | x (xx.x)         | x (xx.x)       |
|        | Loss in VA AND Haemorrhage AND IRF/SRF | x (xx.x)           | x (xx.x)         | x (xx.x)       |
|        | Haemorrhage AND IRF/SRF                | x (xx.x)           | x (xx.x)         | x (xx.x)       |
| Week n | .....                                  |                    |                  |                |

\*Interval Decisions:

Loss in VA: A loss of VA of >=5 letters or more than the best VA recorded since treatment started (Where VA loss is considered, by the investigator, to be due to disease activity);

Haemorrhage: New retinal haemorrhage;

IRF/SRF: Intensive Arm: The presence of any intra-retinal fluid or sub-retinal fluid on OCT  
Relaxed Arm: The presence of any intra-retinal fluid or sub-retinal fluid >200 µm in height at foveal centre?

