**Table 14.2-24 Proportion of Patients showing intra-retinal / sub-retinal fluid, by visit**

Full Analysis Set

|               |   | Intensive
(N=X)
n (%) | Relaxed
(N=X)
n (%) | p-value
(Logistic Regression) | Total
(N=X)
n (%) |
|---------------|---|-----------------------------|---------------------------|----------------------------------|-------------------------|
| Screening     | Intra-retinal Fluid                         | x (xx.x)                    | x (xx.x)                  | x.xxx                            | x (xx.x)                |
|               | No Intra-retinal Fluid                      | x (xx.x)                    | x (xx.x)                  | x.xxx                            | x (xx.x)                |
|               | Intra-retinal Fluid – Center Involvement    | x (xx.x)                    | x (xx.x)                  | x.xxx                            | x (xx.x)                |
|               | No Intra-retinal Fluid – Center Involvement | x (xx.x)                    | x (xx.x)                  | x.xxx                            | x (xx.x)                |
|               | Sub-retinal Fluid                           | x (xx.x)                    | x (xx.x)                  | x.xxx                            | x (xx.x)                |
|               | No Sub-retinal Fluid                        | x (xx.x)                    | x (xx.x)                  | x.xxx                            | x (xx.x)                |
|               | No Intra-retinal Fluid or Sub-retinal Fluid | x (xx.x)                    | x (xx.x)                  | x.xxx                            | x (xx.x)                |
|               | Intra-retinal Fluid OR Sub-retinal Fluid    | x (xx.x)                    | x (xx.x)                  | x.xxx                            | x (xx.x)                |
|               | Intra-retinal Fluid AND Sub-retinal Fluid   | x (xx.x)                    | x (xx.x)                  | x.xxx                            | x (xx.x)                |
| Baseline      | Intra-retinal Fluid                         | x (xx.x)                    | x (xx.x)                  | x.xxx                            | x (xx.x)                |
|               | No Intra-retinal Fluid                      | x (xx.x)                    | x (xx.x)                  | x.xxx                            | x (xx.x)                |

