Patients withdrawn from the study prior to completion of the 24 month assessment visit will be asked to return for an Early Discontinuation evaluation 30 days +/- 7 days following their last study visit.

SCN = Screening, BSL = baseline, INITIAL 3 TR. = Initial 3 treatments at 4 weekly intervals both arms, Flexible interval Tr = treatment intervals will differ based on arm and disease activity, Pr. EP = Primary Endpoint, EOS= End of study.

Figure 1 Study design

2 Project standards

Treatment groups for the analysis

The group labels for the 2 treatment groups for the analysis are: “Intensive” (Group I) and “Relaxed” (Group II).

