2.4 Assessment windows, baseline and post baseline definitions, missing data handling

Assessment windows to be applied to this study are detailed in Table 2.4-3.

Table 2.4-3 Study Assessment Windows

Period	Screen	Initial Treatment				Treatment Period			
		1	2	3	4	n	Month 12	n	Month 24 or Early Discontinuation
Weeks (relative to Baseline, Day 0)	-2 to 0	Baseline	4	8	v	52	v	104	
Visit window (days)			± 3	± 3	± 7	± 14	± 7	± 14	

n = number of visits as required per study protocol² section 5.5.4.1

v = variable. The number of visits will differ dependent on treatment interval as per study protocol³ section 5.5.4.1

2.4.1 Baseline and post-baseline definitions:

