2.8.2 Statistical hypothesis, model, and method of analysis

Statistical methodologies for efficacy variables are detailed in Table 2.8.2-1 (Primary efficacy), Table 2.8.2-2 (Secondary efficacy) and Table 2.8.2-3 (Exploratory efficacy).

Table 2.8.2-1 Primary and Key Secondary Efficacy Analyses

Study Endpoint	Method of Analysis
Mean change in BCVA from baseline to months 12 and 24	1. Mixed Modelling (Refer to Section 2.8.2.5) 2. Summary statistics of change from baseline will be presented.
Mean change in central retinal thickness (CRT) from baseline to months 12 and 24	1. Mixed Modelling (Refer to Section 2.8.2.5) 2. Summary statistics of change from baseline will be presented.
Mean number of injections from baseline to months 12 and 24	1. Binomial Model 2. All data will be listed.

Table 2.8.2-2 Additional Secondary Efficacy Analyses

Study Endpoint	Method of Analysis
Geographic Atrophy from Baseline to Month 12 / 24 (newly developed geographic atrophy between baseline and Month 24 (Yes/No))	1. Logistic regression model (Refer to Section 2.8.2.8) 2. Survival Analysis (Refer to Section 2.8.2.10)
Geographic Atrophy from Baseline to Month 12 / 24 (Change in area of geographic atrophy from the visit where geographic atrophy was first present)	1. Mixed Modelling (Refer to Section 2.8.2.8)
Proportion of patients showing greater than or equal to 15 letters (EDTRS) gain from baseline to month 24	1. Logistic regression model (Refer to Section 2.8.2.8)
Proportion of patients showing less than 15 letters loss from baseline to month 24	1. Logistic regression model (Refer to Section 2.8.2.8)
Proportion of patients showing no IRF and SRF at month 2, 12 and 24	1. Logistic regression model (Refer to Section 2.8.2.8)

Table 2.8.2-3 Exploratory Efficacy Analyses

Study Endpoint	Method of Analysis
Proportion of patients with SRF, as assessed by the █████ CRC, and IRF, as assessed by investigators at Baseline, who do not resolve their SRF and IRF by Month 24	1. Logistic regression model (Refer to Section 2.8.2.8)
The proportion of patients with a) SRF b) IRF c) both SRF and IRF d) neither SRF or IRF at baseline, 2, 12, 24 months	1. Logistic regression model (Refer to Section 2.8.2.8)

Proportion of patients with SRF at baseline who never resolve their SRF at any visit up to Month 2, 12 and 24 (irrespective of their IRF)	1. Logistic regression model (Refer to Section 2.8.2.8)

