2.8.2.1 Descriptive Summaries

All data will be listed.

All continuous data will be summarised by timepoint and treatment group using descriptive statistics. All categorical data will be summarized by timepoint (if appropriate) and treatment group by the number (and percentage) of patients in category.

For all patients, data will be recorded on scheduled visits for treatment. These visits are based on a bi-weekly visit grid, however each patient has their own set of scheduled visits which are determined by disease activity/visual impairment. Therefore, the number of visits differs between patients and as a consequence the number of available assessments/data at each visit differs. The time course of efficacy variable data will be presented/summarized as per the observed scheduled visits. As this differs between patients “by visit” tables presenting the overall time-course will be based on a biweekly time-grid.

Endpoints for BCVA improvement or BCVA loss will be summarized by presenting the number and percentage of patients in each treatment achieving the endpoint.

The mean BCVA value will be presented graphically by time point and treatment group, categorized by baseline BCVA value. The baseline categories will be: -0.29-0.00, 0.01-0.30, 0.31-0.60, 0.61-0.90, 0.91-1.20 and 1.21-1.50. The same graph will be presented for the mean BCVA change from baseline.

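### Fluid p-values at the in-between weeks of shell Table 14.2-24, and under stated conditions the any-visit test of never-resolved SRF to Months 12 and 24, can be significant when fluid is identical in both arms

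*SAP*

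**What the plan says.** **Visits.** SAP Table 2.4-3 fixes baseline, Weeks 4 and 8, and Months 12 and 24 for everyone. Between these, "The number of visits will differ dependent on treatment interval". SAP 2.8.2.1 adds that "each patient has their own set of scheduled visits which are determined by disease activity/visual impairment", and the legend to SAP Figure 1 says "treatment intervals will differ based on arm and disease activity".

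**Trigger.** The footnote to shell Table 14.2-7 (the shells are the document supplied as the protocol) counts any intra-retinal fluid (IRF) or SRF as activity in the Intensive arm. For the other arm it reads "Relaxed Arm: The presence of any intra-retinal fluid or sub-retinal fluid >200" µm in height at the foveal centre. Visual acuity loss and new haemorrhage apply to both arms.

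**Who is analysed.** SAP 2.4.1.2 uses only patients measured at the time point, without imputation.

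**Tests by visit.** The shell table titled "Proportion of Patients showing intra-retinal / sub-retinal fluid, by visit" (14.2-24) has a logistic p-value column that is filled in the Week n rows. SAP 2.4.1.3 makes visit names fortnightly after Week 12. SAP Table 2.8.2-3 asks for tests of SRF, IRF, both, or "neither SRF or IRF at baseline, 2, 12, 24 months". Under Descriptive Summaries, SAP 2.8.2.1 says that "tables presenting the overall time-course will be based on a biweekly time-grid".

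**Any-visit tests.** SAP 2.8.1 counts patients with baseline SRF who "never resolve their SRF at any visit up to Month 2, 12 and 24". Shell Table 14.2-25 gives an odds ratio and p-value at each of those months. LR_3 in SAP Table 2.8.2.8-1 is similar but requires both fluids at baseline. Neither model has a term for the number or timing of visits.

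**The concern.** An eye with shallow SRF and no other trigger counts as active in the Intensive arm and not in the Relaxed arm. So after Week 8, who is seen in a given week depends on fluid status through a rule that differs by arm. Randomisation does not protect a comparison of the patients who happen to be seen in Week 14 or Week 20. In the same way, the arm with more visits has more chances of a single dry reading, which is all it takes to leave the never-resolved group.

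A p-value from either source could be read as an effect of the regimen on SRF, which is what the two regimens are meant to treat differently. These outputs are exploratory or supportive, so the risk is a misread mechanism and not a wrong primary conclusion.

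**Working it through.** **1. Benchmark.** The plan states no error rate for the fluid tests beyond two-sided 0.05 (SAP 2.1). The stated 165 per arm is used as given. It is consistent with margin 5, SD 15 and 80% power: 2 × (1.960 + 0.842)² × 15²/5² ≈ 141.3, so 142 per arm. For 15% dropout, 142/0.85 gives 168 and 142 × 1.15 gives 164.

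**2. Who is seen first after Week 8.** The interval rule is in study protocol section 5.5.4.1, which was not supplied. Assume that an active eye returns after 4 weeks and an inactive eye after 6. Leaving aside the other triggers:

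| Visit | Intensive eyes seen | Relaxed eyes seen |
|---|---|---|
| Week 12 | IRF or any SRF at Week 8 | IRF, or SRF above 200 µm at the centre |
| Week 14 | no IRF and no SRF at Week 8 | no IRF; shallow SRF allowed |

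At Week 14 SRF must look rarer in Intensive. At Week 12 IRF must look rarer in Intensive, because eyes with only shallow SRF dilute it. IRF at Week 14 is not distorted, since both groups were free of IRF at Week 8.

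In one simulated pattern with identical fluid, Week 14 showed SRF in 12% of 58 Intensive and 39% of 116 Relaxed eyes, about 7 of 58 and 45 of 116. The log odds ratio is ln[(45/71)/(7/51)] = 1.53, with SE √(1/7 + 1/51 + 1/45 + 1/71) = 0.446, so z = 3.43. That pattern was rejected in 97% of trials. At Week 32 the direction had reversed (40% v 29%).

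**3. Null simulation.** Inputs:
- 165 per arm; 15% dropout, unrelated to fluid; the same fluid process in both arms.
- Baseline values from the example totals in shell Table 14.1-10: SRF 286/347 = 82%, IRF or cyst 214/347 = 62%, SRF above 200 µm 3/23 = 13%.
- Eight fluid patterns and two interval rules (4 to 12 weeks in 2-week steps; if active, 2 weeks shorter or back to 4), with a 5% other trigger in both arms.
- A treatment-only Wald test; 2,000 trials per combination (Monte Carlo SE 0.5 points at 5%).

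Rejection in Table 14.2-24:
- SRF row: median over in-between weeks 6.3% to 46.1%; Week 14, 39% to 99.8%.
- IRF row: median 6.2% to 43.9%; Week 12, 24% to 100%; Week 14, no excess.
- SRF presence at Months 2, 12 and 24, one definition: 3.9% to 6.2%.

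Further runs with dry spells of only about 2 to 4 weeks left the average weekly rate below 5%, so the excess is possible but not certain.

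**4. Any-visit SRF.** If a persistently wet eye reads dry at a fraction p of visits, independently, the chance of no dry reading in k visits is (1 − p)^k. One simulated case averaged 21.6 v 15.6 visits. With p = 5% this gives 33% v 45%; with p = 10%, 10% v 19%. Simulated rejection:

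| | Month 12 | Month 24 |
|---|---|---|
| Four patterns without lasting shallow SRF | at most 5.1% | at most 5.1% |
| Four patterns with 15% to 30% of eyes lastingly wet, dry at 5% to 10% of visits | 9.3% to 18.9% | 15.6% to 38.9% |
| LR_3 (both fluids at baseline) | up to 12.2% | up to 21.8% |
| LR_9, at least one fluid persists | up to 11.4% | up to 21.4% |
| LR_9, both persist | at most 3.6% | at most 3.6% |
| LR_8 (IRF), readers agree | at most 5.5% | at most 5.5% |

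The case with 21.6 v 15.6 visits had 9.3% v 16.8% never resolved. At Month 2 rejection was 3.8% to 6.4%. In separate runs where SRF cleared once and stayed clear there was no excess; adding 3% grading error gave 16% and 17% at Months 12 and 24.

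**5. Control and remedy.** With one trigger for both arms, average in-between-week rejection was 2% to 5%, and never-resolved SRF 1% to 4% at Month 12 and 0% to 6% at Month 24. This isolates the arm-specific trigger as the cause. With the planned triggers but non-resolution counted only at visits common to both arms, rejection was 3% to 5% at Months 12 and 24.

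**6. Grading.** SAP 2.8.1 has the reading centre grade fluid by the definition of each arm. If Relaxed SRF counted only above 200 µm, the same fluid would read as 31% to 54% v 1% to 30% at Month 12.

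**The case against.** **Week n is template text.** Shell Table 14.2-19 also prints Week 4 and Week n rows for geographic atrophy, which SAP 2.8.1 assesses only at baseline, Week 8 and Months 12 and 24. On this view the SAP already gives the answer. That supports the fix, but the p-value column remains in the shell and would be programmed.

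**Reading-centre and investigator gradings differ.** Efficacy uses reading-centre data (SAP 2.1), while the site CRF records fluid separately. In the example figures of Table 14.1-10, IRF is 37.5% by the centre (61.7% with cysts) but 77.2% by CRF. If investigators call IRF more often, both arms return early and the SRF asymmetry is masked. In one set of runs any-visit rejection fell from 16% and 28% at Months 12 and 24 to 7% and 12%; in another, from 10–12% and 15–22% to 5–7% and 3–11%. The excess at in-between weeks remained. This stands, and limits the second part. It also works the other way: if investigators missed 60% of centre-graded IRF and dry spells were short, never-resolved IRF (LR_8) was rejected in 13% to 16% at Month 24; with 30% missed, 5% to 8%.

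**The null is artificial.** Injection and visit intervals are equal (SAP 2.6), so the null needs extra injections to leave fluid unchanged. That is right for testing validity, but it is not a forecast.

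**Grading visits are not defined.** SAP 2.8.1 does not list the visits at which the centre grades fluid. Both parts assume that it grades at the variable visits, as the by-visit table and the any-visit endpoint imply.

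**Conclusion.** The first part holds. From Week 12, the in-between p-values in Table 14.2-24 compare differently selected subsets and go beyond the SAP. The second part holds conditionally: never-resolved SRF to Months 12 and 24 (Table 14.2-25, LR_3, and LR_9 only if its event is at least one fluid persisting) can be inflated if SRF persists with intermittent dry readings or grading error. The documents do not fix the size, because the interval rule and fluid patterns are assumed.

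A reader might infer more than this:
- That the any-visit test will falsely favour Intensive. It need not: there is no excess without such persistence, and arm-specific grading would reverse the direction and become the main cause.
- That every fluid test fails. Month 2 is unaffected, and presence at Months 12 and 24 is compared at visits scheduled for all, subject to dropout and one definition of fluid.
- That LR_8 is safe in all cases. It is safe only if investigator and reading-centre IRF gradings agree.
- That the primary result is at risk. Change in BCVA is assessed at Month 24, a visit scheduled for all patients, and is unaffected.

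The change should be made, with medium confidence in the size of the problem.

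**What to change.** - **Table 14.2-24:** print between-arm p-values only at baseline and Months 2, 12 and 24, and label all other weeks descriptive.
- **Never-resolved SRF at Months 12 and 24** (Table 14.2-25, LR_3): for the between-arm test, count non-resolution only at Weeks 4 and 8 and Months 12 and 24, up to the month tested. Show the any-visit proportion descriptively, beside the visits per arm already summarised under SAP 2.6. Keep the Month 2 test.
- **LR_9 and Table 14.2-27:** state whether the event is both fluids persisting or at least one; if at least one, treat it in the same way. Applying the common-visit definition to LR_8 is a safe check.
- **Grading:** state that between-arm fluid tests use one definition for both arms, and reconcile this with SAP 2.8.1.
- **LR_3:** reconcile its both-fluids population with SAP 2.8.1 and Table 14.2-25, which take baseline SRF irrespective of IRF.
- **Optional GEE and random-intercept models** (SAP 2.8.2.6 and 2.8.2.8): limit any between-arm test to the common visits.

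The cost is wording in the shells and SAP, with no new data. The common-visit definition ignores dry readings at other visits, so it gives higher never-resolved proportions, but a formal test is kept.
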